	Placebo: Saline Solution 0.9%						
	Dose: N/A						
	Route: Intravenous						
	Regimen: Weeks 0, 4, 8, 16, 24 and 32.						
Duration of administration	1 hour						
Laboratory Samples.	Screening, Week 0, 24 and 52.						
Visits by Weeks	Screening						
	Week 0 – Infusion 1						
	Week 4 – Infusion 2						
	Week 8 – Infusion 3						
	Week 16 – Infusion 4						
	Week 24 – Infusion 5						
	Week 32 – Infusion 6						
	Week 42 – Follow Up.						
	Week 52 – End of Study						

"A Randomized, Double-Blind, Single Center, Phase 2, Efficacy and Safety Study of autologous HB-adMSCs vs Placebo for the Treatment of Patients with Parkinson's Disease"

Introduction

Objectives

Primary Objective:

• To investigate the safety and efficacy of intravenous infusions of HB-adMSCs vs Placebo in patients with Parkinson's disease as determined by improvements in Quality of Life as measured by the MDS UPDRS assessment. (Time frame: Baseline to Weeks 4, 8, 16, 24, 32, 42 and 52).

Secondary Objective:

• To evaluate the safety and efficacy of intravenous infusions of HB-adMSCs vs Placebo in patients with Parkinson's disease as, determined by changes in disease assessments and dosage of medications. (Time frame: Baseline to Weeks 4, 8, 16, 24, 32, 42 and 52).

Endpoints

Primary Endpoints

The safety and efficacy endpoints of this study will be evaluated by assessing changes from Baseline to Weeks 52 in the following:

- Changes in MDS-UPDRS Part II from Baseline to Week 52. Motor Aspects of Experiences of Daily Living (M-EDL), including speech, saliva and drooling, chewing and swallowing, eating tasks, dressing, hygiene, handwriting, doing hobbies and other activities, turning in bed, tremor, getting out of bed, a car, or a deep chair, walking and balance and freezing.
- Incidence of treatment-emergent Adverse Event (TEAEs) and serious Adverse Events (SAEs).
- Incidence and risk of AEs of special interest (serious or nonserious), including thromboembolic events, peripheral events defined as, thromboembolism of the extremities, also infections and hypersensitivities.
- Clinically significant changes in laboratory values, vital signs, weight and physical examination results.

Secondary Endpoints

The safety and efficacy endpoints of this study will be evaluated by identifying changes from Baseline to Weeks 4, 8, 16, 24, 32, 42 and 52 in the following:

- Changes in MDS-UPDS Part I, III, IV, or total score.

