• To investigate the safety and efficacy of intravenous infusions of HB-adMSCs vs Placebo in patients with Parkinson's disease as determined by improvements in Quality of Life, estimated by the MDS UPDRS assessment. (Time frame: Baseline to Weeks 4, 8, 16, 24, 32, 42 and 52). A battery of statistical tests will be applied, where suitable and applicable. Tests will include the report of parametric or non-parametric statistical tests, with the corresponding p-values, presented in pair-wise manner, as well as contingency tables, representing answers in their native form.	 Change from Baseline in Total MDS-UPDRS Part II, only at Week 52 Number of treatment-emergent Adverse Event (TEAEs) during 52 week period Number of serious Adverse Events (SAEs) during the period of 52 weeks Number of AEs of special interest includes thromboembolic events, peripheral events defined as thromboembolism of the extremities, infections and hypersensitivities Change from baseline in clinical parameters, measured at the end of the study (52 weeks): Physical examination Electrocardiogram (ECG) Pulse Systolic blood pressure Body weight BMI Change from baseline in laboratory assessments at the end of the study (52 weeks):

Protocol Number: HBPD03

Date: 18-Apr-2023 Version: 2.0 Hope Biosciences Statistical Analysis Plan Status: Final

Objectives	Endpoints
	o Biochemistry
	 Haematology
	 Urinalysis
Secondary Objectives	Secondary Endpoints
To evaluate the safety and efficacy of intravenous infusions of HB-adMSCs vs Placebo in patients with Parkinson's disease based on	Change from Baseline in MDS- UPDRS Total score, at all the timepoints collected, during the period of study (52 Weeks)
changes in disease assessments and dosage of medications. (Time frame: Baseline to Weeks 4, 8, 16, 24, 32, 42 and 52).	 Change from Baseline in Total MDS- UPDRS Part I, at all the timepoints collected during the period of study (52 Weeks)
	 Change from Baseline in Total MDS- UPDRS Part II, at all the timepoints collected during the period of study (52 Weeks)
	 Change from Baseline in Total MDS- UPDRS Part III at all the timepoints collected during the period of study (52 Weeks)
	 Change from Baseline in Total MDS- UPDRS Part IV, at all the timepoints collected during the period of study (52 Weeks)
	 Change from Baseline in Total Neuro- Quality of Life Assessments scores (Neuro-QOL), at all the timepoints collected during the period of study (52 Weeks)

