5.4 Multiple Comparisons and Multiplicity

The multiplicity adjustment will be performed for key efficacy endpoints for the conclusion. The Bonferroni-Holm method is used for the multiplicity adjustment for the hypothesis tests performed for the efficacy endpoints. The multiplicity adjusted for the hypothesis tests for below endpoints,

- Change from Baseline in Total MDS-UPDRS Part I at Week 52
- Change from Baseline in Total MDS-UPDRS Part II at Week 52
- Change from Baseline in Total MDS-UPDRS Part III at Week 52
- Change from Baseline in Total MDS-UPDRS Part IV at Week 52
- Change from Baseline in Total Neuro-Quality of Life Assessments scores (Neuro-QOL) at Week 52
- Change from Baseline in Total Parkinson's disease fatigue scale (PFS-16) at Week
 52
- Change from Baseline in Total Parkinson's disease Questionnaire (PDQ-39) at Week 52
- Change from baseline in Total VAS score at Week 52

Using the Bonferroni-Holm method the p-values will be ordered in increasing order and starts with testing the hypothesis with the lowest p-value on the 2.5/k% level (two-sided), where k is the number of hypotheses in the procedure. If significant, the testing proceeds to comparing the next lowest p-value with 2.5/(k-1)%. The testing will stop at the first non-significant result.

Due to high number of performed tests, the additional statistical corrections will be included in order to correct the p-value and avoid false positive results. As the observed phenomena are biological in nature, p-values will be also examined in such manner that the focus will be on the biological meaning. Both methods are providing more rigorous p-values and help avoiding the false positive interpretations.

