5.6 General Considerations

Unless otherwise stated, all hypotheses will be tested at 0.95% confidence interval (p = 0.05, two-sided test, when applicable). In other words, statistical test will look for the difference (either better results or worse results), rather than focusing solely on efficacy. All continuous measurements will be summarised descriptively at each visit, followed by treatment, using observed data.

Summary of continuous variables will be presented using the total number of participants (N), Mean, Standard Error of mean (SE), Standard Deviation (SD), Median and Range (Minimum and Maximum). The categorical variables will be presented using the number and the percentage of subjects who have provided the defined categorical answer.

For measurements obtained during course of time, mean values will be plotted to explore the trends. Observed data will be used as the basis for plotting data along with standard error (SE) or Standard Deviation (SD) represented as bars, if not otherwise specified.

A non-parametric Mann-Whitney U Test (or Wilcoxon Rank-Sum Test) will be applied on primary and secondary efficacy endpoints to test the significance of the effects of the treatment by comparing median values.

For measurements performed over time, median values will be plotted to explore the trends. Observed data will be used as the basis for plotting the data along with Inter Quartile Range (IQR) used as bars, if not otherwise specified.

A parametric, repeated measurements ANOVA will be applied as a sensitive analysis to test the significance of the effects of the treatment.

Change from baseline safety Lab measurements will be analyzed using a repeated measurements ANOVA to test the significance of the effects of the treatment.

Presentation of results from a statistical analysis model will include the estimated means caused by treatment effects, using Adjusted Mean. HB-adMSCs 200MM vs Placebo group will be compared.

For all endpoints analyzed statistically, estimated mean treatment differences will be presented together with two-sided 95% confidence intervals and p-values.

All safety evaluations will be presented using Safety analysis set while the efficacy analysis

Individual safety and efficacy parameters will be listed.

will be presented using Efficacy analysis set.

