8.2. Clinical Laboratory Analyses

Laboratory evaluations including the analyses of Biochemistry laboratory tests (includes Comprehensive Metabolic Profile), Hematology laboratory tests (Complete Blood Count

Statistical Analysis Plan

(CBC) and Coagulation Panel) and Urinalysis. The details of the planned displays are in **Error!** Reference source not found...

All laboratory parameters, including numerical urine analysis parameters will be summarised descriptively. Categorical urine analysis results will be summarized using count and percentage based on subjects. Differences in safety Lab parameters after the treatment was applied are tested using the Mann-Whitney U (or Wilcoxon Rank-Sum) Test.

Distribution of laboratory test results will be presented using scattered box-plot.

Change from baseline laboratory measurements available at post-baseline at scheduled measurements will be analyzed using Repeated Measures ANOVA. The model will include treatment, visits as fixed factors. The within subject factor is visit and with 2 levels (Weeks 24 and 52). The between-subjects factor is treatment (HB-adMSCs 200MM or Placebo).

Results of urine pregnancy test will be listed only in the individual subject data listings.

Individual laboratory evaluations will be listed. In addition, a listing containing individual subject laboratory values outside the normal reference ranges will be provided separately.

Data recorded at unscheduled assessments will not be included in tables and figures but will be listed.

8.3. **Other Safety Analyses**

The analyses of non-laboratory safety test results, including physical examination and vital signs. The details of the planned displays are presented in Error! Reference source not found..

Physical Examination and Vital signs will be summarized using count and percentage based on subjects. The vital signs based on visit and change from baseline will be summarized using descriptive statistics.

Individual Vital signs, Physical Examination evaluations will be listed.

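### Numerical laboratory analytes, a primary safety endpoint, get two significance tests at a nominal 5% with no main method and no specified multiplicity rule, so chance findings and conflicting p-values are likely

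*SAP*

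**What the plan says.** **Status of the endpoint.** The SAP's table of objectives and endpoints places "Change from baseline in laboratory assessments at the end of the study (52 weeks" in the primary block, before the secondary objectives. The protocol's Primary Endpoints also include laboratory values, but worded as "Clinically significant changes in laboratory values, vital signs, weight and physical examination results".

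**Tests ordered.** SAP 5.6 names one method: "Change from baseline safety Lab measurements will be analyzed using a repeated measurements ANOVA to test the significance of the effects of the treatment". SAP 8.2 names two. First, "Differences in safety Lab parameters after the treatment was applied are tested using the Mann-Whitney U (or Wilcoxon Rank-Sum) Test"; no visit is given, nor whether raw values or changes are compared. Second, "Change from baseline laboratory measurements available at post-baseline at scheduled measurements will be analyzed using Repeated Measures ANOVA", with treatment and visit as factors and two visits, Weeks 24 and 52.

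**Ranking.** For efficacy, SAP 7.1.4.1 and 7.2.4.1 make Mann-Whitney the analysis and the ANOVA a sensitivity analysis, to be dropped if normality is clearly violated. Section 8.2 has no such ranking and no normality condition.

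**Error control.** SAP 5.6 sets a two-sided 0.05 level for all hypotheses unless otherwise stated. SAP 5.4 says "The Bonferroni-Holm method is used for the multiplicity adjustment for the hypothesis tests performed for the efficacy endpoints" and lists eight endpoints, none of them a laboratory variable. The last paragraph of 5.4 promises further p-value corrections because many tests are run, without naming a method or the tests covered.

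**Not tested.** Categorical urine results are counted, and the pregnancy test is only listed (8.2).

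**The concern.** Two tests on the same analyte, with no main one, leave the laboratory result undefined whenever the p-values fall on opposite sides of 0.05. The tests also address different questions. A Mann-Whitney test at Week 52 would look at that visit alone. The ANOVA treatment effect, in a model with treatment and visit and no interaction mentioned, averages Weeks 24 and 52. Neither is declared to be the analysis of the Week 52 endpoint.

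The number of tests adds to this. A metabolic panel, a blood count and coagulation tests yield many analytes. Each is judged at 5% twice, and no stated rule says how an isolated significant result is to be read.

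What is at stake is the laboratory safety conclusion of a 24-patient trial. A chance finding could be reported as a laboratory effect, and a non-significant result at 12 per arm could be taken as reassurance that it cannot give. The efficacy conclusion is not affected.

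**Working it through.** The documents state no laboratory error rate, analyte count or laboratory power, so there is no figure of the plan's own to reproduce.

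**Inputs from the documents**
- Level: 0.05, two-sided (SAP 5.6).
- 12 subjects per arm (Protocol, Investigational Product Assignment).
- Laboratory visits in the model: Weeks 24 and 52 (SAP 8.2).

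**Assumptions**
- K numerical analytes: 20 to 40, with 45 as a further check.
- Correlation between analytes: 0 to 0.6.
- Correlation between a subject's Week 24 and Week 52 changes: 0.5 (0.3 and 0.8 also tried).
- No true effect, normal data, no missing data.
- Mann-Whitney applied to the Week 52 change, the visit of the primary endpoint.

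**Step 1: one method, independent analytes.** P(at least one p<0.05) = 1 − 0.95^K; expected number = 0.05 × K.
- K = 20: 64%, 1.0 expected.
- K = 30: 79%, 1.5 expected.
- K = 40: 87%, 2.0 expected.

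**Step 2: both methods.** Null simulation, 12 per arm. The ANOVA treatment effect is equivalent to a t-test on each subject's mean of the two changes. Chance of at least one p<0.05 by either method (600 runs per cell):

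| Between-analyte correlation | K = 20 | K = 30 | K = 45 |
|---|---|---|---|
| 0 | 81% | 90% | 97% |
| 0.3 | 71% | 80% | 90% |
| 0.6 | 45% | 57% | 67% |

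A separate simulation for K = 20 to 40 over the same correlations gave 48% to 96%. The low ends, 45% and 48%, are compatible: simulation error at 600 runs is √(0.45 × 0.55 / 600) ≈ 2 points. The mean number of distinct analytes with a false p<0.05 was about 1.3 (K = 20) to 3.0 (K = 40), that is 1.3/20 = 6.5% to 3.0/40 = 7.5% per analyte. A skewed (lognormal) check at K = 30 and correlation 0.3 gave 76%, against 80% with normal data.

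**Step 3: disagreement between the methods.** Under the null, Week 52 Mann-Whitney and the ANOVA fell on opposite sides of 0.05 for about 3.5% to 5.5% of analytes. Of analytes significant by either method, 55% to 76% were significant by only one. For K = 20 to 40, the chance of disagreement on at least one analyte was about 44% to 87%. As a check on the independent case, 5% disagreement per analyte gives 1 − 0.95^20 = 64% and 1 − 0.95^40 = 87%.

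**Step 4: what strict adjustment would cost.** Power for a true 1-SD shift, normal approximation: Φ(√(12/2) − z) with √6 = 2.449.
- Unadjusted, z = 1.960: Φ(0.489) = 69%.
- First Holm step, K = 20, level 0.05/20 = 0.0025, z = 3.023: Φ(−0.574) = 28%.
- K = 30, level 0.0017: 24%.
- K = 45, level 0.0011, z = 3.261: Φ(−0.812) = 21%.

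The normal approximation is slightly generous at this sample size, so the true figures are somewhat lower.

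**The case against.** The strongest reply is that no formal decision rests on these p-values. The only formal hypothesis in SAP 2.3 is MDS-UPDRS Part II at Week 52. The protocol's laboratory endpoint turns on clinical significance, which the principal investigator judges, and its study stopping rules are event-based. SAP 5.6 already plans mean differences with 95% confidence intervals for endpoints analysed statistically. SAP 8.2 plans descriptive summaries, box-plots, listings and a separate out-of-range listing. Unadjusted laboratory screening is common and can be sound. All this stands, and it limits the consequence. It does not remove the gap, because the SAP never calls the laboratory tests descriptive. The exploratory label in 2.3 is attached to secondary endpoints, while the SAP lists laboratory change as primary. Adverse events and vital signs receive descriptive summaries only.

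A reader might infer more than the documents support:
- **That false signals are almost certain.** This needs many weakly correlated analytes, or Mann-Whitney at both visits. With correlation 0.6 the risk can be near one half.
- **That several analytes would be flagged by chance.** Counting every p-value, with Mann-Whitney at both visits, gives 2.8 to 5.6 for 20 to 40 analytes, but this can count one analyte up to three times. The number of distinct analytes under the Week 52 reading is about 1.3 to 3.0.
- **That every laboratory result is tested.** Categorical urine results and the pregnancy test are not.
- **That the plan rules out any adjustment.** SAP 5.4 promises a further correction and is not explicit that it is for efficacy only. The accurate criticism is that this correction is unspecified.
- **That the sponsor would pick the convenient p-value.** The plan leaves that open; nothing in it shows intent.

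**Conclusion.** The concern holds in this form: a primary safety endpoint is tested by two methods at a nominal 5%, with no main method, no visit or scale for one of them, no executable multiplicity rule for laboratory data, and no rule for conflicting results. With no true effect, at least one false p<0.05 has a chance of about 48% to 96%, and disagreement between the methods on at least one analyte about 44% to 87%. These ranges rest on an assumed 20 to 40 analytes, correlation of 0 to 0.6 between them, 12 complete subjects per arm, and Mann-Whitney read as a Week 52 test of change. The finding that the method is undefined depends on none of these assumptions. As planned, the p-values do not support a laboratory safety conclusion in either direction.

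**What to change.** Amend SAP 5.6 and 8.2 together:
- Name one laboratory analysis: the between-arm difference in change from baseline at Week 52, with an estimate and 95% CI per numerical analyte. Section 5.6 already provides for estimates and intervals, so this mainly selects among planned outputs.
- Label it descriptive. Delete the second test, and the clause in 5.6 that gives significance testing as the purpose of the laboratory ANOVA.
- State that no single analyte p-value, significant or not, decides laboratory safety.
- Keep the descriptive summaries at each visit, the box-plots and the out-of-range listing.
- In 5.4, say that the further correction does not apply to laboratory data.

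Do not require Holm or another strict adjustment of laboratory p-values: power for a 1-SD shift would fall from about 69% to 21–28%, a poor exchange in a safety screen.

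Cost: wording and fewer outputs, with no new data or patients. The sponsor loses laboratory p-values that can be quoted as significance tests, and the two-visit ANOVA output.

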- Investigational product administration by delegated study personnel: HB-adMSCs or Placebo should only be administered intravenously with a dosing rate of 4-5ml/min and vital sign monitoring of two hours post-drug exposure. Monitoring time may be prolonged if decided by principal investigator. The monitoring of vital signs shall be the same as represented in Figure 8.
- 24 hours after administration of the investigational product, study participants will be contacted by telephone call to assess the incidence of adverse events.

Visit 8 – Safety Follow Up

- Update medical history and concomitant medications if any change occurred since last visit.
- Measure vital signs including respiratory rate, body temperature, blood pressure, pulse rate, oxygen saturation and weight.
- Physical examination by Principal Investigator, including clinical assessments such as MDS-Unified Parkinson's Disease Rating Scale and other assessments included in Table 3.
- Completion of neuro-quality of life questionnaire by study's participant and handwriting assessments.
- Assess the incidence of any adverse event since last visit.

Visit 9 – End of Study

- Update medical history and concomitant medications if any change occurred since last visit.
- Measure vital signs including respiratory rate, body temperature, blood pressure, pulse rate, oxygen saturation and weight.
- Physical examination by Principal Investigator, including clinical assessments such as MDS-Unified Parkinson's Disease Rating Scale and other assessments included in Table 3.
- Completion of neuro-quality of life questionnaire by study's participant and Handwriting assessments.
- Collection of laboratory samples, including Comprehensive Metabolic Panel (CMP), Complete Blood Count (CBC), Coagulation Panel and Urine pregnancy test if female of childbearing potential.
- A video documenting study participant walking and standing from sitting will be recorded during this visit.
- Assess the incidence of any adverse event since last visit.

Unscheduled Visits

The Investigator may at his/her discretion arrange for a study participant to have an unscheduled visit (UNS). Some of the circumstances by which a study participant will be called for a UNS visit are:

- Adverse events (AEs) that require follow-up.
- Collection of laboratory samples for safety reasons.
- Procedures missed at previous study visits.

All unscheduled visits should be documented in the study's participant source.

Trial Assessments

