5.2 Baseline Definitions

For all endpoints, the baseline value will be the value obtained at the latest pre-treatment assessment visit (a non-missing value), including those from unscheduled visits. For example, if an assessment has been made both at screening visit (Visit 1) and infusion 1 visit (listed as Visit 2, Week 0), the value from the later, "infusion 1 visit" is used as the baseline value, if the value is collected prior to the admission of infusion. If the value measured at the Week 0 visit is missing or if it was collected on/after the dose and the assessment has been made at screening/unscheduled visits (which is prior to Week 0 visit), then the screening/unscheduled visits value is used as the baseline value.

Unless otherwise stated, if baseline data is missing, no derivation will be performed, and baseline will be set to missing.

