7.1.4.1. Statistical Methodology Specification

Primary endpoint will be analyzed using the Mann-Whitney U Test (or Wilcoxon Rank-Sum Test) for the comparison of HB-adMSCs 200MM vs. Placebo.

Sensitivity analysis

Sensitivity analysis will be performed on Efficacy analysis set using a repeated measurements ANOVA model to evaluate the robustness of using parametric method. If the normality of dataset shows significant violation from the presumption of normality, the parametric method will not be performed.

All primary endpoint efficacy measurements available at post-baseline at scheduled measurements will be analyzed using Repeated Measures ANOVA. The model will include treatment, visits as fixed factors. The within subject factor is visit and with 7 levels (Weeks 4, 8, 16, 24, 32, 42 and 52). The between-subjects factor is treatment (HB-adMSCs 200MM or Placebo).

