10.1.2.1. Handling of Missing Data for Statistical Analysis

Element	Reporting Detail
efficacy endpoints	• For all analyses of the Efficacy analysis set, missing value imputation will not be performed and participants' data will be excluded from any statistical analyses due to missing data.

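### SAP 8.2 keeps unscheduled laboratory results out of the by-arm tables, although the protocol uses unscheduled visits for safety draws and for missed procedures

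*SAP*

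**What the plan says.** The protocol's section on unscheduled visits gives, among the reasons for one, "Collection of laboratory samples for safety reasons" and "Procedures missed at previous study visits". Scheduled laboratory samples after baseline fall only at Weeks 24 and 52 (protocol Table 3).

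SAP 8.2 ends its account of laboratory data with "Data recorded at unscheduled assessments will not be included in tables and figures but will be listed". On the model it says "Change from baseline laboratory measurements available at post-baseline at scheduled measurements will be analyzed using Repeated Measures ANOVA", with visit as a two-level factor, Weeks 24 and 52. Values outside the reference range go to a separate individual-subject listing.

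Laboratory change has primary status in both documents. The protocol's primary endpoints include clinically significant laboratory changes. The SAP's table of objectives and endpoints puts change from baseline in laboratory assessments at 52 weeks under the primary objective.

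Three other rules bear on the point:

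- **Baseline.** SAP 5.2 accepts pre-treatment values "including those from unscheduled visits".
- **Repeated values.** SAP 10.2.2.2 covers efficacy and safety, and takes the last non-missing measurement at a post-baseline visit. It does not say to which visit an unscheduled value belongs.
- **Adverse events.** The protocol asks that a laboratory abnormality be documented as an adverse event. SAP 8.1 ends the treatment-emergent window 3 days after the last day of infusion treatment and puts events outside it in listings.

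**The concern.** Two kinds of laboratory result are lost from the comparison between arms. The first is a make-up draw: the participant missed the scheduled sample, the site obtained it later as the protocol allows, and the value still cannot enter a table. The second is a sample drawn because the investigator was worried. Such samples are more likely than routine ones to show a clinically significant change, and they are the ones confined to listings.

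The SAP text describes no by-arm count of participants with a clinically significant or out-of-range value. A reader of the tables would see by-visit summaries at two planned time points, and would have to reconstruct the abnormal results by arm from the listings. In a trial of 12 per arm, a few such participants could change the impression of safety.

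**Working it through.** The plan states no figure on this point, so there is none to reproduce. The check follows what happens to each kind of result and then measures the gaps.

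**1. Where each result goes under the SAP as written**

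| Laboratory result | Laboratory tables, figures, ANOVA (8.2) | Adverse event tables (8.1) |
|---|---|---|
| Week 52 draw missed, made up at an unscheduled visit, normal | No | Not applicable |
| Abnormal on an unscheduled draw, onset from first infusion to 3 days after the last | No | Yes, if recorded as an adverse event |
| Abnormal on an unscheduled draw, later onset, non-serious | No | No, listing only |

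The last row assumes that the event has complete dates and does not lead to withdrawal. SAP 8.1 treats events with missing dates as treatment-emergent, and it tabulates serious events and those leading to withdrawal. The laboratory Mann-Whitney test in 8.2 carries no scheduled-only wording, but I read its output as table content and so as subject to the exclusion.

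**2. Size of one lost make-up draw**

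Allocation is 12 and 12 (protocol, randomization section). One participant is 1/12 = 8.3% of an arm.

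**3. Length of the period with neither route**

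- Last infusion at Week 32: 32 × 7 = day 224.
- Window closes: 224 + 3 = day 227.
- End of study at Week 52: 52 × 7 = day 364.
- Uncovered: 364 − 227 = 137 days, or 137/364 = 38% of the study.

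With ±7 days at both visits, the range is (357 − 231 − 3) = 123 to (371 − 217 − 3) = 151 days. For a participant who stops infusions early, the window closes earlier.

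**4. What the scheduled draws can see**

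Nominal weeks from each infusion to the next later scheduled draw, assuming the Week 24 sample is taken before that day's infusion:

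| Infusion week | Next scheduled draw | Gap (weeks) |
|---|---|---|
| 0 | 24 | 24 |
| 4 | 24 | 20 |
| 8 | 24 | 16 |
| 16 | 24 | 8 |
| 24 | 52 | 28 |
| 32 | 52 | 20 |

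The shortest gap is 8 weeks. A change that appears and resolves between scheduled draws would be caught only by an unscheduled sample. If the Week 24 sample were taken after the infusion, that infusion alone would have a same-day draw; the other five rows would not change.

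**5. Consistency within the SAP**

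If an unscheduled laboratory value is the last non-missing one at a visit, 10.2.2.2 selects it for summary and analysis while 8.2 bars it from tables. The two need reconciling.

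**The case against.** **The adverse event route.** Laboratory abnormalities are to be recorded as adverse events, and treatment-emergent events are tabulated by arm. This stands up to 3 days after the last infusion, so it would be wrong to say that abnormal unscheduled results appear only in listings throughout. It does not cover the remaining 137 or so days, and it does nothing for a normal make-up value. One may say that this late gap comes from the treatment-emergent cut-off. That is true, but 8.2 is what closes the other route.

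**By-visit means should not be mixed with triggered draws.** This stands. Samples taken because of symptoms would distort a visit mean, so a rule keeping them out of those means is sound. It does not justify keeping them out of every table.

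**The planned displays cannot be read.** The SAP's references to its display lists are broken, so a by-arm abnormality table might be planned there. This stands as a limit on what can be verified. Such a table would still fall under the 8.2 exclusion.

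**The baseline rule is no contradiction.** Accepting an unscheduled value as the last one before dosing is compatible with scheduled-only summaries afterwards. This also stands, and nothing here rests on it.

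**A stronger reading for efficacy.** A reader might infer that make-up values of the primary endpoint also drop out. The documents do not support this:

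- The exclusion sentence sits in the laboratory section.
- The wording "All primary endpoint efficacy measurements available at post-baseline at scheduled measurements will be analyzed using Repeated Measures ANOVA" governs the sensitivity analysis. The primary and secondary Mann-Whitney tests have no such limit.
- SAP 10.2.2.2 can be read as keeping make-up values.
- The ±7 days in protocol Table 3 is a visit window. Nothing in the SAP text excludes a value obtained outside it.
- The rule that "missing value imputation will not be performed and participants' data will be excluded from any statistical analyses due to missing data" would matter only if a make-up value counted as missing, which the SAP does not say.

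Nor should a large loss be inferred for the sensitivity ANOVA. The Efficacy analysis set requires all 6 infusions, so its members attended every infusion visit, and a whole visit can be missed only at Week 42 or 52. If complete data were required and misses were independent at an assumed 2%, 5% or 10% per visit, 1 − (1 − p)² gives 4%, 10% or 19%. A single form could still be missed at an infusion visit.

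**Conclusion.** The point holds for laboratories. Under SAP 8.2 as written, make-up and safety-triggered draws are outside the by-arm laboratory tables, figures and ANOVA, and the adverse event tables are only a partial substitute. For about 137 days (123 to 151 with visit windows), a non-serious, fully dated abnormality found on an unscheduled draw and not leading to withdrawal is in neither set of tables.

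By-arm reporting of clinically significant laboratory change may therefore be understated. That is a risk, not a demonstrated bias: the values stay in listings, and the documents do not say how many unscheduled draws to expect. The conclusion rests on the SAP text, because the display lists are not readable.

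For efficacy, the defect is only that no rule says to which visit a make-up assessment belongs. The documents do not say that retrieved primary-endpoint values are discarded.

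**What to change.** 1. **Add one by-arm safety table.** Report participants with any clinically significant or out-of-range post-baseline laboratory value, as worst post-baseline value or shift, including unscheduled samples. Keep by-visit means on scheduled or assigned values.
2. **Amend the sentence in SAP 8.2.** Assign a draw made only because the scheduled one was missed to that scheduled visit. Pre-specify a window with a lower and an upper limit that does not overlap the neighbouring visit; an open-ended window would not suit an endpoint set at Week 52. Word the choice between several values so that it agrees with 10.2.2.2.
3. **Clarify efficacy.** State that the same assignment applies to make-up efficacy assessments, in the Mann-Whitney tests and the repeated measures ANOVA alike, and that the 8.2 exclusion concerns laboratories only.

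The rule should be fixed before anyone applying it has seen results by arm, since SAP 5.5 gives some sponsor members unblinded interim results. The cost is a few lines of SAP text and one table. The downside is slightly more spread in the actual timing of assigned values, which can be listed.
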